#### **3.2 Provider Profiling**

Before beginning patient-level data collection, each institution lead will be asked to fill out a provider profiling questionnaire on the local caseload, catchment populations, management frameworks and resources available at pre-hospital, emergency department, ward, surgical and ICU phases of TSI care.

#### **3.3 Data Set**

A data set will be collected on all adult patients admitted after TSI within the 30-day inclusion period. This will be split into five sections: (i) initial injury and admission data, (ii) imaging data, (iii) injury management, (iv) operative data (if applicable) and (v) outcome data. The dataset was developed and refined through iterative consultation with clinicians caring for TSI in low and high HDI countries.

### 3.4 Duration of Study

Local study teams may pick any 30-day period between the 6-month study period to conduct the study. Teams must follow patients for up to 6-weeks post-admission or until they are discharged or die (whichever event occurs first). For example, if a team selects 1/6/2021 as their start date, they must include all patients who meet the inclusion criteria between 1/6/2021 and 30/6/2021. Moreover, if a patient is admitted during the inclusion period on 30/6/2021 they should be followed up until the 11/8/2021 or until discharge or death (whichever event occurs first).

### 3.5 Study measures

The following categories of routine clinical data will be collected prospectively for all patients included in the study. The full data set is included in *Appendix A*.

#### Initial injury and admission data

- Baseline demographics e.g. age, gender
- Type and mechanism of injury
- Pre-hospital timeline, transfers and transportation
- Clinical presentation on arrival to hospital e.g. GCS, Kampala Trauma Score, Frankel grade
- Initial injury details
- Admission details

#### Imaging data

- Imaging modalities utilised for radiological characterisation of injury
- Injury classification e.g. AO Spine classification

#### Injury management data

- Intended injury management
- Injury management during transfer e.g. immobilisation
- Specialised therapies received e.g. physiotherapy, speech and language therapy

#### Operative management (where applicable)

Where included patients underwent operative management, these details will be collected prospectively. However, operative management is not a prerequisite for inclusion in the study.

- Details of the operating team
- Duration, location and type of operation

- Intra-operative course and complications
- Funding

### Outcome Data

Outcomes will be measured up to 6-weeks or until death/discharge (whichever event occurs first). This follow-up period was selected after consultation with experienced clinicians from high and low HDI settings to balance the aim of capturing significant short-term outcome events with practicalities of robust data collection across centres. This is supported by literature suggesting that over half of patients are typically lost to follow-up, with significantly increased barriers to follow-up in LMICs, and that early outcomes assessed within shorter time frames, particularly in these settings, remain significant and useful. A range of outcomes after traumatic spinal injury will be assessed including:

- Frankel grade at 6-weeks post-admission (or at discharge, whichever event occurs first). This has been demonstrated as a feasible measure to collect in both high and low resource settings.
- 6-week mortality
- Length of stay (LOS)
  - Hospital
  - Intensive Care Unit
- Perioperative complications (where applicable)
  - Return to operating theatre during follow-up period
  - Surgical site infection (SSI)
  - Adverse events of special interest e.g. pressure ulcer, pneumonia, deep venous thrombus
- Functional status at 6-weeks or discharge
  - Independence with activities of daily living
  - Mobility

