### 10.5 Outcome Data

Death within the 6-week follow-up period?	
 
• Yes
 
• No
 
 
If Yes:
 
 
• Date of death: dd/mm/yyyy
 
• In ICU at time of death? Yes/No
 

Discharged within the 6-week follow-up period?	
 
• Yes
 
• No
 
 
If Yes:
 
 
• Date of discharge: dd/mm/yyyy
 
• Destination of discharge: 
 
○ Transfer to another hospital
 
○ Transfer to a rehabilitation unit
 
○ Usual place of residence/Home
 
○ Absconded
 
○ Other (specify _____)
 
 
 

Was the patient admitted to intensive care at any point during the 6-week follow up period?	
 
• Yes
 
• No
 
 
If Yes:
 
 
• Date of admission to ICU: dd/mm/yyyy
 
• Was the patient discharged from ICU during the 6-week follow up period? Yes/No
 
 
If Yes:
 
 
• Date of discharge from ICU: dd/mm/yyyy
 

Was the patient intubated during admission?	
 
• Yes
 
• No
 

Did the patient require a tracheostomy?	
 
• Yes
 
• No
 

Was the patient requiring ventilatory support at time of death/the end of the 6-week follow up period (whichever event occurs first)?	
 
• Yes
 
• No
 

Did any adverse events of special interest occur in the 6-week follow-up period? (Select all that apply)	
 
• None
 
• Pressure Ulcer
 
• Pneumonia
 
• Pulmonary embolism
 
• Deep venous thrombosis
 
• Decubitus Ulcer
 

	
 
• Urinary tract infection
 
• Symptomatic haematoma
 
			
Did any surgical site infections occur in the 6-week follow-up period?	
 
• Yes
 
• No
 
 
If Yes:
 
 
• Required antibiotics only
 
• Required debridement
 
• Required removal of metalwork
 
			

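### The plan lists 6-week mortality, but follow-up ends at discharge and the outcome form does not state that cut-off consistently, so deaths after discharge may be counted unevenly across sites

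*Combined protocol and SAP*

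**What the plan says.** Section 3.5 (Outcome Data) sets the window: "Outcomes will be measured up to 6-weeks or until death/discharge (whichever event occurs first". Section 3.4 gives sites the same duty: "Teams must follow patients for up to 6-weeks post-admission or until they are discharged or die (whichever event occurs first". The reason is stated openly: the period was chosen to "balance the aim of capturing significant short-term outcome events with practicalities of robust data collection across centres", and the section cites loss to follow-up, with greater barriers in low- and middle-income countries.

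The list beneath that statement includes "6-week mortality". In the same list the Frankel and functional-status items each mention discharge; the mortality item does not. The Overview, section 1.2 and section 5 speak of early mortality, which is not defined.

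Appendix A 10.5 asks "Death within the 6-week follow-up period" and "Discharged within the 6-week follow-up period", with dates for both events ("Date of discharge: dd/mm/yyyy" for the second). Discharge destinations include "Transfer to another hospital", a rehabilitation unit and absconding.

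Section 5 plans to analyse early mortality by HDI group, with random effects of site and country, and to compare outcomes between sites by a median odds ratio. Section 6 excludes worldwide epidemiology, indications or efficacy, and long-term outcomes. It does not mention deaths between discharge and six weeks.

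**The concern.** The outcome name promises vital status at six weeks for every patient. The design supplies it only for those who die in the institution or are still inpatients at day 42. For everyone else, observation stops on the day they leave, including those who leave for another hospital.

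Two things follow. First, a figure reported as 6-week mortality would describe a quantity that the study does not systematically measure. Second, the number recorded may depend on the site as well as the patient: on how early the site discharges or transfers, and on whether staff who hear of a later death enter it. If either differs by HDI group or by site, part of a reported mortality difference could come from discharge practice or recording. The validation process in section 4.2 checks case ascertainment and operations; it does not check deaths.

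**Working it through.** **1. The window.** Six weeks is 42 days. The example in section 3.4 agrees: admission on 30 June 2021 plus 42 days is 11 August 2021. The clock is not in question; the stopping rule is.

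**2. The form, field by field (Appendix A 10.5).**

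- Death, adverse events, surgical site infection: the period is called the six-week follow-up period, with no mention of discharge.
- Discharge: asked as an event within that same period.
- Ventilatory support: assessed at death or the end of the six-week period; discharge is omitted.
- Frankel grade: assessed at the end of the six-week period, or at death or discharge if earlier.
- Survival: follow-up is expressly defined as ending at six weeks or discharge, whichever is first.

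Take a patient discharged on day 10 whose death on day 20 becomes known to the site. Reading the death field as a fixed six weeks gives Yes to death. The survival field gives Yes to surviving follow-up. A site that applies section 3.4 throughout answers No to death. Section 5 does not say which field is analysed.

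**3. Effect of uneven recording.** The documents give no mortality, length of stay, proportion discharged or post-discharge risk, so every input here is assumed. Let d = 5% die before discharge, a = 80% be discharged alive before day 42, q = the risk of dying between discharge and day 42, and f = the share of those later deaths that a site records.

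Recorded mortality = d + a × q × f. With q = 2%:

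- f = 0: 5.0%
- f = 0.5: 5.0 + 80 × 0.02 × 0.5 = 5.8%; odds ratio against f = 0 is (5.8/94.2)/(5.0/95.0) = 1.17
- f = 1: 5.0 + 80 × 0.02 = 6.6%; odds ratio (6.6/93.4)/(5.0/95.0) = 1.34

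With f = 1, the odds ratio is 1.17 at q = 1% and 1.70 at q = 4%. If half the sites record none and half record all, the standard deviation of site log-odds at q = 2% is ln(1.34)/2 ≈ 0.147. The median odds ratio is then exp(√2 × 0.6745 × 0.147) ≈ 1.15, by a normal approximation, with no true difference between sites.

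**4. Effect of discharge timing.** Suppose no site records later deaths and both groups show 5%, with 90% of one group and 60% of the other discharged alive. True 42-day risk = 5% + a × q.

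- q = 2% in both: 6.8% v 6.2%, odds ratio 1.10
- q = 0 v 4%: 5.0% v 7.4%, odds ratio 0.66
- q = 4% v 0: 8.6% v 5.0%, odds ratio 1.79
- q = 0 in both: odds ratio 1.00

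The recorded odds ratio is 1.00 in all four cases. The hidden difference can go either way or be absent.

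**The case against.** The best reply is that the plan already bounds the outcome. The discharge cut-off is disclosed and justified, and the sentence setting it introduces the list in which mortality stands. That is right: the cut-off is not a fault, and a reader who inferred a concealed or unjustified design choice would be wrong. But the Frankel and functional items repeat the qualifier and the mortality item does not, and the unqualified name is the one likely to be carried into a report.

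A reader might also infer that the form contradicts itself. The documents do not show that. An event can fall within a period and also end it, as death does, so the fields can be read consistently with section 3.4. Nor does the appendix show all the platform's logic, so a check on conflicting answers cannot be excluded. What stands is an ambiguity that sites may resolve differently.

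Next, dates of death and discharge are collected and curation precedes analysis, so one date comparison would remove stray later deaths. This is correct, and it makes the repair easy, but the plan does not state the rule. It cannot recover deaths that were never observed, nor help the adverse-event and infection fields, which carry no event date. Identifying fields such as date of birth and time of injury are collected, but no linkage of transferred patients is described.

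Finally, the illustrations rest on assumed inputs, some of them extreme. That stands too. They show that distortion is possible; they do not show that it occurs.

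**Conclusion.** The point holds as a mismatch between the outcome's name and what is measured, together with form wording that permits uneven recording. Reporting the result as 6-week mortality would overstate what the study observes.

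Distortion of the HDI and between-site comparisons is possible but not demonstrated. It requires deaths after discharge, and either recording or discharge timing (or post-discharge risk) that differs by setting. A reader might infer that one HDI group's mortality is understated by a known amount; the documents support neither a size nor a direction. The odds ratio of 1.34 for full against no recording depends entirely on the assumed 5%, 80% and 2%.

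The primary descriptive objective is unaffected. This concerns a secondary outcome and should be fixed because the remedy is cheap and changes what may be concluded.

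**What to change.** 1. In section 3.5, section 5 and Appendix A 10.5, name the outcome *death before discharge from the participating institution, within 42 days of admission*. Do not report it as 6-week mortality.
2. State the discharge cut-off in the death, adverse-event and surgical-site-infection fields, and say in section 5 which field supplies the mortality outcome. The ventilatory-support field can be aligned in the same edit.
3. Add a data rule: a death dated after the discharge date is kept out of this outcome and listed separately. Both dates are already collected. For adverse events and infections only the wording can settle the matter.
4. Report length of stay and discharge destination by HDI group and site beside mortality, so that readers can see how far observation time differed.
5. Add to section 6 that deaths after discharge or transfer within six weeks are not systematically captured.

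Optional: an analysis treating live discharge as a competing event (cause-specific hazards), and a sensitivity range that adds the proportion discharged alive times an assumed post-discharge risk, allowed to differ by HDI group.

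The required items cost some wording, one data rule and one table, with no new data. The price is the loss of a 6-week mortality headline and slightly more reporting.

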## 4. Data Capture and Validation

### 4.1 Data Capture

Collected data will be stored exclusively on a secure web-based system within the Outcome Registry Intervention and Operation Network (ORION) platform: <https://orion.net/login>. This will enable secure data collection, validation and storage in a standard format (SQL) which is compliant with National Health Service security standards (including the Information Governance Toolkit). All patient data will be transmitted and held anonymously. A pilot will be conducted using the platform to assess feasibility prior to rolling out the full study.

### 4.2 Data Validation

A number of steps have been taken to ensure validation of all data entered.

- I. The dataset, web-based case report forms, and curation process has been designed according to DAQCOR principles.
- II. Web-based forms in the ORION platform contain fixed options at the point of data entry to maximise the likelihood of accurate and complete data capture at the point of collection.
- III. A local data validator independent to the local study team will be appointed at every participating institution. They will have access to a separate platform on Orion to ensure blinding to the rest of the data collected at their institution. They will be asked to complete a two-phase validation process, with a specific ORION validation user guide available to guide them through the process.
  - a. Prospective Case Acquisition: During the selected 4-week inclusion period, the local data validator will be asked to independently identify and collect all patient cases suitable for inclusion in the study. For validation, they will be required to prospectively collect these cases, recording the admission date, age at admission and AO injury type. This will subsequently be correlated with the data collected by their local team by the central study team.
  - b. Retrospective Operative Data: At 10 weeks from the start of the inclusion period (6-weeks following the end of the inclusion period), the local data validator will be asked to independently access operating theatre logs over the preceding 10 weeks. They will be required to document all the patients who have had an operation for TSI during this period and input the date and type of operation into the validation system where this corresponds to a patient admitted during the inclusion period. This will be used by the central study team to validate this specific cohort of their institution's cases.

## **5. Statistical Analysis**

Anonymised data will be analysed by the central study team. Fundamentally the main analysis will consist of a quantitative description of case-mix and the variations in processes of care. Identification and description of areas where known best practice is lacking or unavailable will be performed. This will enable identification of potential targets for future implementation studies.

In addition, early outcomes will be assessed to identify case-mix and process factors that may form a substrate for intervention. Participating centres will be stratified based on their country into groups based on their Human Development Index (HDI). The Human Development Index is calculated for each country based on its life expectancy at birth, years of schooling and gross national income (GNI) per capita.

Specifically, after data validation and curation, the primary analysis will comprise of (1) statistical descriptive analysis of patient-level registry variables, (2) characterisation of processes of care using statistical descriptions of both provider profiling data and patient-level process variables followed by a description of typical process groupings. This will follow and extend methodologies that have previously been applied successfully to traumatic brain injury. Case-mix and process analysis will be stratified in a nested way by site, country, and association with human development index (HDI).

Analysis for the secondary objectives will consist of a quantitative statistical summary of non-operative and operative management. Intra- and inter-site variances will be compared and associations with HDI and process of care factors sought.

Whilst only short-term outcomes can be obtained in this pragmatic point-study, outcomes analysis will be attempted for early mortality, functional status as assessed using the 5-point Frankel Grade, neurology, adverse events and trajectory from admission to 6 weeks post-injury (or discharge or death, whichever occurs first). These will be analysed by HDI group in an appropriate nested model accounting for random effects of site and country. Either ordinal models (for statistical power) or dichotomised models will be used depending on the statistical properties of the data and suitability of model assumptions. Mixed effects models will be used to assess the relationship between HDI and deterioration in functional status at 6 weeks while controlling for confounding variables.

Associations between patient factors and processes of care will be sought with recognised indicators of evidence-based good practice to identify patient profiles associated with efficacious treatment trajectories. Using methodology previously successfully applied to TBI, process of care variables from both the registry and provider profiling will be collated with estimates of variability to inform a future Delphi consensus process aimed at defining process of care performance indicators that are feasible, measurable, and globally relevant.

Provider profiling summary statistics will be compared with current evidence-based best practice to identify gaps and associations with process of care, case-mix, site and HDI will be explored using standard statistical approaches. Variability in guideline availability and any association with TSI care will be assessed by comparing provider profiling and registry data using methodology conducted previously for TBI.

The data, along with catchment area data from provider profiling will be used to obtain point estimates with confidence intervals to provide a high-level description of the epidemiology of TSI across the sites studied using routinely available population data. A similar methodology that has been applied to the study of chronic subdural haemorrhage will be utilised.

A *p*-value of less than 0.05 will be considered statistically significant, correction for multiple comparisons will not be undertaken. A median odds ratio approach will be used to compare variations in outcomes between sites correcting for explanatory features discovered in the descriptive part of the analysis.

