**10.3 Injury Management**

What was the intended injury management?	
 
● No intervention
 
● Non-operative
 
● Operative
 

Was there immobilisation during transfer?	
 
● Nothing
 
● Collar
 
● Trauma board
 
● Bed
 

Did the patient have surgical bedrest?	
 
● Nothing
 
● Bedrest, no logroll
 
● Bedrest + logroll
 
● Collar only
 

Traction?	
 
● Yes
 
● No
 

Did the patient receive any specialist therapy as an inpatient	
Yes No
 
If Yes, what type of therapy was provided?
 
 
- Speech and Language Therapy
 
- Tracheostomy care
 
- Physiotherapy
 
- Occupational therapy
 
- Alternative therapy – Ayurveda etc
 
- Other (specify _____)
 

Was spinal surgery performed?	
 
● Yes, performed at this institution
 
● Yes, transferred to a different institution for surgery
 
● No
 

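### Section 5 seeks process factors linked to early mortality, but surgery, ICU admission, therapy and tracheostomy are ever/never fields and no method handles the time before receipt

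*Combined protocol and SAP*

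**What the plan says.** Section 5 (Statistical Analysis) gives as an aim that "early outcomes will be assessed to identify case-mix and process factors that may form a substrate for intervention". For the secondary objectives it adds that "Intra- and inter-site variances will be compared and associations with HDI and process of care factors sought". It then states that "outcomes analysis will be attempted for early mortality, functional status as assessed using the 5-point Frankel Grade, neurology, adverse events and trajectory".

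On modelling, the section says of these outcomes: "These will be analysed by HDI group in an appropriate nested model accounting for random effects of site and country". It continues: "Either ordinal models (for statistical power) or dichotomised models will be used". A mixed model relates HDI to functional deterioration. A median odds ratio compares sites, adjusted for whatever explanatory features the descriptive work turns up; these are not limited to features fixed at admission. No model of outcome on surgery, ICU care or therapy is written down. There is no time zero, landmark or time-dependent term.

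Appendix A shows how the processes are recorded:

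- 10.3 asks "Was spinal surgery performed" and "Did the patient receive any specialist therapy as an inpatient". The therapy item has no date. A separate item records intended management, without a timestamp.
- 10.4 holds the operation date, but is completed only for surgery at the same institution.
- 10.5 asks whether the patient was in intensive care at any point in the 6 weeks (with dates) and whether a tracheostomy was required (no date). Dates of death and discharge are recorded.

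Sections 3.4 and 3.5 end follow-up at 6 weeks, discharge or death, whichever is first. Section 1.2 includes an objective on patient profiles that predict the efficacy of interventions, whereas section 6 says the protocol is not designed to study the efficacy of specific management.

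**The concern.** A patient who dies on day 2 while waiting for an operation is filed under no surgery and, very likely, no therapy. A patient with the same plan who lives to day 5 and is operated on is filed under surgery. The treated group is thus guaranteed to have survived its wait, and deaths during the wait are charged to the untreated group. This is immortal-time bias. It appears even when the treatment does nothing, and a binary or ordinal outcome at a fixed horizon cannot remove it.

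The results are meant to point to targets for intervention. The bias grows with waiting time, which may well differ by site and by HDI group, the contrasts the study is built around. Section 5 tests at p < 0.05 without multiplicity correction, so a spurious association has little to stop it. Putting ever/never processes into the adjustment set for the between-site median odds ratio would bring the same problem into that comparison.

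**Working it through.** The documents give no mortality, waiting time, operation rate or length of stay, so there is no figure of the plan's to reproduce. Apart from the 42-day window (6 weeks, section 3.4), every input below is an assumption.

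**Inputs.** True effect of surgery: none. Mortality by day 42: 10%. Intended for surgery: 60%. Wait: exponential, median 1, 3 or 7 days. Death hazard: constant, or front-loaded (Weibull shape 0.6). A patient counts as operated if the wait is shorter than the time to death and than 42 days.

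**One case by hand** (constant hazard, median wait 7 days, no discharge):

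- Death rate h = −ln(0.9)/42 = 0.00251 per day; surgery rate μ = ln(2)/7 = 0.0990 per day.
- P(operated | intended) = μ/(μ+h) × (1 − exp(−42(μ+h))) = 0.9753 × 0.9859 = 0.9616.
- P(operated and alive at day 42 | intended) = 0.9 × (1 − exp(−42μ)) = 0.9 × 0.9844 = 0.8859.
- P(operated and dead | intended) = 0.9616 − 0.8859 = 0.0756.
- Times 0.6: operated 0.0454 dead, 0.5316 alive. Not operated: 0.1 − 0.0454 = 0.0546 dead, 0.9 − 0.5316 = 0.3684 alive.
- Odds ratio = (0.0454/0.5316)/(0.0546/0.3684) = 0.58, although surgery has no effect.

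**Simulation, no discharge** (2,000,000 patients per setting; 30% of patients severe with three times the hazard, treatment unrelated to severity). Ever/never odds ratio for death:

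| Median wait | Constant hazard | Front-loaded deaths |
|---|---|---|
| 0 days | 1.00 | 1.00 |
| 0.25 days | 0.98 | 0.88 |
| 1 day | 0.92 | 0.74 |
| 3 days | 0.76 | 0.56 |
| 7 days | 0.57 | 0.40 |

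At 20% mortality the values lie within about 0.02 of these. For a therapy planned in 90% of patients with a median start of 2 or 4 days, the odds ratio is 0.56 or 0.38 with constant hazard and 0.30 or 0.21 with front-loaded deaths. Without discharge, grouping by intended management or by status at a day-3 landmark gives 0.99 to 1.01.

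**Follow-up ended at discharge**, as the protocol requires. Discharge is exponential with median 7 or 14 days, counted from surgery in intended patients and from admission in others; waits are 1 to 7 days. Repeat runs agree within about 0.02.

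| Analysis | Estimate (truth 1.00) |
|---|---|
| Ever/never odds ratio | 0.24 to 0.89 |
| Intended-management odds ratio | 1.06 to 1.95 |
| Day-3 landmark odds ratio | 0.64 to 1.00 |
| Time-dependent exposure, discharge censored (cause-specific rate ratio) | 0.99 to 1.01 |

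Intended management fails here because intended patients stay longer and so have longer to die under observation. The fixed-horizon landmark fails because those still waiting on day 3 stay longer than those never intended for surgery. If discharge is instead unrelated to treatment (median 7, 14 or 28 days), the ever/never odds ratio is 0.51 to 0.72 with front-loaded deaths and 0.78 to 1.01 with constant hazard, so the bias can cancel.

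**Confounding by severity added** (90% of severe and about 47% of other patients planned for surgery; 10% mortality; no discharge). Ever/never odds ratio, constant hazard then front-loaded:

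| Median wait | Odds ratio |
|---|---|
| 0 days | 1.68, 1.68 |
| 1 day | 1.48, 1.14 |
| 3 days | 1.18, 0.82 |
| 7 days | 0.83, 0.54 |

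Intended-management and landmark odds ratios stay between about 1.2 and 1.7: they remove the immortal time but not the confounding.

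**The case against.** The strongest reply is that the plan contains no such model. The outcome models spelled out have HDI group as the exposure, which is fixed at baseline, and the main analysis is descriptive. Section 6 disclaims efficacy. This is right as far as it goes: the defect is an unspecified analysis, not a wrongly specified one. The aim is nevertheless stated, mortality is among its outcomes, the fields available are ever/never, and section 1.2 pulls against section 6.

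A reader might infer that these processes will come out looking protective. The documents do not support that. Preferential treatment of severe patients can push the odds ratio above 1, and discharge can offset the bias or enlarge it. Only the direction of the immortal-time component is predictable.

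A reader might also take the phrase "to identify patient profiles associated with efficacious treatment trajectories" as a second process-outcome analysis. In section 5 that sentence relates patient factors and processes to recognised indicators of good practice, not expressly to death or Frankel grade.

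Nor are all process variables exposed. Provider profiling, transport mode and immobilisation during transfer are settled by arrival. The admission location item in 10.1 includes HDU and ITU, so some ICU care starts at time zero with little or no immortal time.

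Finally, the intended-management field looks like a complete cure. It is not: it has no timestamp, and once follow-up ends at discharge it can be biased itself.

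**Conclusion.** The concern holds for processes received after a wait: surgery, later ICU admission, specialist therapy and tracheostomy. Section 5 intends to use early mortality to pick process factors as intervention targets and gives no way of handling the time before receipt. With no true effect, an ever/never odds ratio for death of 0.40 to 0.92 arises without discharge, and 0.24 to 0.89 in the treatment-dependent discharge scenario above. These ranges illustrate size and do not predict this study's results. They rest on assumed mortality, operation rate, waits and lengths of stay, without confounding, and they concern mortality only. The net direction in the real data cannot be known in advance. The HDI models and the descriptive case-mix analysis are not affected. Section 5 should be amended before the process-outcome analyses are run.

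**What to change.** Amend section 5 as follows.

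(a) For mortality, set admission as time zero. Enter surgery and ICU admission as time-dependent exposures from their recorded dates in a cause-specific hazard model, with discharge as a competing (censoring) event and site and country effects kept. Operation, ICU admission and death are dated to the day only, so state a rule for same-day events. A landmark analysis is a sensitivity analysis only, with its day varied and discharge handled the same way.

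(b) A comparison by intended management (10.3) may be added as a secondary analysis, also with discharge handled explicitly, noting that the field has no timestamp.

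(c) Describe specialist therapy, tracheostomy and surgery after transfer out (no operation date) without relating them to mortality. Do not relate ever/never surgery or ICU admission to mortality either, and use none of these as adjusters in the between-site median odds ratio for mortality.

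(d) State that confounding by severity remains, and reconcile the efficacy objective in section 1.2 with the disclaimer in section 6.

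The dates needed for (a) are already collected. The cost is SAP wording, modest extra analysis work, and less precision for transferred patients.
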